3.2.3 Baseline definitions

3.2.3.1 MAD baseline

MAD baseline will be used for the MAD and MAD+LTE analysis periods. It is defined as the last non-missing measure prior to the first dose of study drug in the MAD, except in the instances given below:

For vital signs (blood pressure [BP] and heart rate [HR]), baseline will be defined as the
average of the triplicate values collected on Day 1 pre-dose in the MAD. If only one or
two assessments are available, the single assessment or average of the two assessments
will be used.

- o For ECG continuous parameters, baseline will be defined as the average of the triplicate values collected on Day -1 of the MAD. If only one or two assessments are available, the single assessment or average of the two assessments will be used. For ECG interpretation, baseline will be defined as the worst categorical results of the triplicate results collected on Day -1 of the MAD.
- For PD biomarkers, baseline will be defined as the average of the Screening and Day 1 pre-dose values in the MAD.
- o For C-SSRS suicidal ideation score, baseline will be defined as the maximum score collected on Day -1 and Day 1 pre-dose in the MAD.

3.2.3.2 Active treatment period baseline

Active treatment period baseline will be used to analyze the LTE Period and the Active Treatment Period. Active treatment period baseline is the same as the MAD baseline for early start subjects, and for late start subjects is the last non-missing measure collected prior to the first dose of study drug in the LTE except in the instances below:

- o For vital signs (blood pressure [BP] and heart rate [HR]), as the average of the triplicate values collected on Day 1 pre-dose in the LTE. If only one or two assessments are available, the single assessment or average of the two assessments will be used.
- For ECG continuous parameters, as the average of the triplicate values collected immediately prior to first dose in the LTE. For ECG interpretation, baseline will be defined as the worst categorical results of the triplicate results collected immediately prior to first dose in the LTE.
- For C-SSRS suicidal ideation score, as the maximum score collected on Day -1 and Day 1 pre-dose in the LTE.

3.2.4 Analytical visits

All post-baseline data will be summarized using the visit labels provided in the data. Multiple results with the same visit label will be averaged for the continuous variables, and the worst result will be used for the categorical variables. Results with visit labels as "Unscheduled" will be presented in data listing, but not be included in the by-visit summary tables and figures, except for determining baseline.

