Visits on Days -1 to 92 (Weeks 1 to 14)

Monthly or quarterly Study Drug administration

(ISIS 814907: placebo, 3:1)

- Each patient will receive 4 doses of Study Drug, (or 2 doses under quarterly dosing interval)
- The first 2 patients at a given dose level will be assigned 1:1 active:placebo, and at least 1 week must elapse before additional patients are enrolled at this dose level. Overall, the randomization in each cohort will be 3:1 active:placebo
- · Cohort enrollment will be staggered
- Initiation of dosing in a higher-dose cohort will occur after (1) the prior cohort is fully enrolled and (2) review of the prior cohort data has been conducted as depicted in the Cohort Enrollment Flowchart below

POST-TREATMENT PERIOD

Visits on Days 113 to 253

(Weeks 17 to 37)

END-OF-STUDY PROCEDURES

or Early Termination from Post-Treatment Period

Day 253

(Week 37)

Patients in Cohorts A and B will have their last visit in the MAD, Part 1 part on Day 253; there will be a variable gap of time between the end of Part 1 and entry into Part 2 for those patients.

Patients in Cohorts C and D will transition seamlessly to LTE, Part 2 of the study with Day 253 in Part 1 corresponding to Day -1 in Part 2

EARLY TREATMENT TERMINATION

Complete block of visits associated with last dose received (see * in Appendix A)

Complete 7-day post-dose follow-up visit/phone call after last dose received

Either

If patient willing to participate in Post-Treatment Period (PTP), conduct Week 17 visit ~4 weeks after last dose and proceed with PTP

Or

If patient is not willing to participate in PTP, conduct Week 37 as an Early Termination Visit

STUDY DESIGN AND TREATMENT SCHEMA FOR LTE, PART 2

REGISTRATION PERIOD*

Days -21 to -2 (Weeks -3 to -1)

Collect informed consent to reconfirm patient eligibility

*for Cohorts A and B patients only;

patients in Cohorts C and D will transition seamlessly into LTE, Part 2 and do not need a registration visit

TREATMENT EVALUATION PERIOD

Visits on Days -1 to 344 (Weeks 1 to 49)

Quarterly administration of ISIS 814907

- Each patient will receive 5 doses of Study Drug, on a quarterly basis
- Patients in Cohorts C and D will seamlessly transition to the LTE part of the Study; Patients in Cohorts A and B will be invited to participate following a positive FSMG from Cohort C to D.

POST-TREATMENT PERIOD

Visits on Days 421 to 449

(Weeks 50 to 64)

END-OF-STUDY PROCEDURES

or Early Termination from Post-Treatment Period

Day 449

(Week 64)

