For patients who terminate early from the Treatment Evaluation Period in Part 1 for reasons other than withdrawal of consent and are not willing to participate in the Post-Treatment Period, every effort should be made to (a) conduct the full block of visits associated with the last dose received (see description of "visit blocks" above), (b) conduct the visit scheduled for 7 days after the last dose received and (c) conduct the Week 37 visit as an Early Termination Visit. Patients who prematurely discontinue the Treatment Evaluation Period, or the Post-Treatment Period, in Part 1 will not be allowed to participate in Part 2.

For patients withdrawn from the study during the Treatment Evaluation Period in Part 2 for reasons other than withdrawal of consent, every effort should be made to encourage the patient to (a) conduct the full block of visits associated with the last dose of ISIS 814907 that would have been received had the patient not withdrawn (see description of "visit blocks" above), (b) conduct the visit scheduled for 7 days after the last dose received, and (c) proceed to the

Week 60 visit approximately 4 weeks after last dose and conduct the next visit in the Post-Treatment Period at Week 64 (see Appendix A).

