- If the patient terminates early from the Treatment Evaluation Period but is willing to participate in the Post-Treatment Period, the patient should complete all visits in the "visit block*" associated with the visit and then proceed to the Week 17 visit approximately 4 weeks after last dose and complete all visits in the Post-Treatment Period. If the patient terminates early from the Treatment Evaluation Period and is not willing to participate in the Post-Treatment Period or if the patient terminates early from the Post-Treatment Period, the patient should complete all visits in the "visit block*" associated with the visit and then proceed to the Week 37 visit as an Early Termination Visit (approximately 4 weeks after the last dose)
- 2 cl = clinic visit; ph = phone visit
- 3 On the Day 1 dosing day, the patient must stay in the clinic overnight and undergo safety monitoring follow-up as scheduled on Day 2. On the other dosing days, the patient may either stay in the clinic overnight or be discharged, provided the patient returns to the clinic on the day after the dosing for all required assessments

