3.4.2 Handling of Missing Data

Unless otherwise specified, missing values will not be imputed.

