3.7.3 Clinical Evaluations

3.7.3.1 Functional Activities Questionnaire (FAQ)

FAQ is used to measure functioning/ability to perform activities of daily living.

In the MAD Period, FAQ total score (actual value, absolute change and percent change from baseline) will be summarized by treatment group and each post-baseline visit at Day 113, 169 and 253 visits using descriptive statistics. The absolute changes from baseline at each post-baseline visit will be compared between each ISIS 814907 treated analysis group and pooled placebo using the ANCOVA with baseline value as a covariate or Wilcoxon Rank Sum test, as appropriate.

In the LTE Period, the actual values, changes and percent changes from baseline at Day 449 visit will be summarized using descriptive statistics.

All FAQ collected scores will be presented in data listings for the MAD and MAD+LTE Periods.

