3.7.3.3 Mini-mental State Examination (MMSE)

The MMSE has five different domains:

- Orientation: a maximum of 10 points, calculated by adding Orientation to Time and Orientation to Place;
- Memory: a maximum of 6 points, calculated by adding Recall and Registration;

- Attention/Calculation: a maximum of 5 points;
- Language: a maximum of 8 points, calculated by adding Naming, Comprehension,
 Repetition, Reading and Writing;
- Visual construction: a maximum of 1 point, which is Drawing.

In the MAD Period, MMSE domain scores and total score (actual value, absolute change and percent change from baseline) will be summarized by treatment group and each post-baseline visit at Day 56, 113, 169 and 253 visits using descriptive statistics. The absolute changes from baseline at each post-baseline visit will be compared between each ISIS 814907 treated analysis group and pooled placebo using the ANCOVA with baseline value as a covariate or Wilcoxon Rank Sum test, as appropriate.

In the LTE and MAD+LTE Periods, the actual results, changes and percent changes will be summarized by analysis group and each post-baseline visit within the period.

All MMSE collected scores will be presented in data listings for the MAD and MAD+LTE Periods.

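### A Part 1 early termination visit is run as the Week 37 visit, and SAP 3.2.4 sorts data by visit label alone, so early values could be analysed as Day 253

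*Combined protocol and SAP*

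**What the plan says.** **How data are placed.** SAP 3.2.4 states: "All post-baseline data will be summarized using the visit labels provided in the data". It gives no study-day windows. The one label it treats differently is Unscheduled; those results are listed "but not be included in the by-visit summary tables and figures, except for determining baseline". The SAP has no rule for ET visits.

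**What the ET visit is.** Appendix A footnote 1 covers a patient who stops during the Part 1 Treatment Evaluation Period and will not enter the Post-Treatment Period. After the current visit block, that patient is to "proceed to the Week 37 visit as an Early Termination Visit (approximately 4 weeks after the last dose"). Protocol 8.9 tells sites to "conduct the Week 37 visit as an Early Termination Visit", and the Part 1 treatment schema says: "If patient is not willing to participate in PTP, conduct Week 37 as an Early Termination Visit". The schedules give Week 37 and ET one shared column, dated Day 253. Footnote 13 places make-up CSF sampling at Day 253 (Week 37) as part of the ET procedures.

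**The other route.** A patient who stops dosing but accepts follow-up goes to the Week 17 visit (nominally Day 113) about 4 weeks after the last dose, then completes the Post-Treatment Period (Protocol 8.9, footnote 1).

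**What is analysed.** FAQ "will be summarized by treatment group and each post-baseline visit at Day 113, 169 and 253 visits using descriptive statistics"; SAP 3.7.3.4 names the same days for NPI-Q. MMSE "will be summarized by treatment group and each post-baseline visit at Day 56, 113, 169 and 253 visits using descriptive statistics"; SAP 3.7.3.2 names the same days for RBANS. At each post-baseline visit, change from baseline in each active group is compared with pooled placebo by ANCOVA or a Wilcoxon test. The population is every randomized and dosed patient (SAP 3.4.1), so early stoppers are not screened out.

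**The concern.** A true Day 253 visit is 24 weeks after the last dose; an ET visit for a patient who stops during treatment is about 4 weeks after it. A label-only rule cannot tell them apart if both carry the Week 37 label. Day 253 is the last Part 1 time point for all four scales, and SAP 1.3.3 also uses them to watch for unexpected worsening. In a progressive disease an early score will tend to understate later decline. Groups are small enough for one score to show, and a mistimed placebo score would enter all four dose comparisons. Vital signs, chemistry, hematology, urinalysis and ECG sit in the same column and are also summarised by visit. RBANS and MMSE are summarised again by visit in the MAD+LTE Period, so the ambiguity recurs there.

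**Working it through.** **Inputs**
- Dosing days: 1, 29, 57, 85 (4-dose) or 1, 85 (2-dose) (Protocol 8.1). SAP 1.1 records that Cohort D used the 2-dose regimen.
- ET visit, or Week 17 visit after an early stop: about 28 days after the last dose (Appendix A footnote 1).
- Day 253 visit: 24 weeks after the last dose (Protocol 3.4.1), window ±7 days (Appendix A).
- Cohorts of 8, 8, 12 and 16 at 3:1 (Protocol 3.1.1).
- ET rate and database labels: not given.

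**The plan's own figure.** 85 + 24 × 7 = 85 + 168 = Day 253, which reproduces.

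**Timing.** Actual day = last dose day + 28. The gap to Day 253 matters for an ET visit, and the gap to Day 113 for a brought-forward Week 17 visit.

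| Last dose | Actual day (about) | Days before Day 253 | Days before Day 113 |
|---|---|---|---|
| Day 1 | 29 | 253 − 29 = 224 | 113 − 29 = 84 |
| Day 29 | 57 | 253 − 57 = 196 | 113 − 57 = 56 |
| Day 57 | 85 | 253 − 85 = 168 | 113 − 85 = 28 |
| Day 85 | 113 | 253 − 113 = 140 | 0 |

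Only the first and last rows apply to the 2-dose regimen. No ET row comes within 7 days of Day 253. Patients who finish dosing and leave later in the Post-Treatment Period are less than 140 days early.

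**Weight of one patient.** Active groups: 6, 6, 9 and 12. Pooled placebo: 2 + 2 + 3 + 4 = 11. Shares: 1/6 = 17%, 1/9 = 11%, 1/12 = 8%, placebo 1/11 = 9%. If the patient is replaced (Protocol 4.3) and both stay in the analysis set: 1/7 = 14%, 1/10 = 10%, 1/13 = 8%, placebo 1/12 = 8%.

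**Illustration only.** Assume linear change from Day 1 to Day 253 and no replacement; neither is given in the documents. An ET value then holds 28/252 = 11% to 112/252 = 44% of the full change. One such patient shrinks the group mean change by (1 − share)/n: 9 to 15% (n = 6), 6 to 10% (n = 9), 5 to 7% (n = 12), 5 to 8% (placebo, n = 11).

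**The case against.** The strongest reply is that the harm hangs on a label the documents do not show. A shared schedule column does not establish a shared database label. If ET visits have their own label, SAP 3.7.3 names the visit days for the four scales, so an ET score would most naturally appear only in the listings. That stands, and it is why the point is conditional. Even so, SAP 3.2.4 does not say where such a result goes, and the general laboratory and vital-sign summaries name no days.

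The affected group is also narrow. The patient must stop during treatment, not withdraw consent, refuse the Post-Treatment Period and still attend an ET visit. For CSF, only make-up samples are involved, and some belong to patients who truly reach Day 253 after a missed lumbar puncture and are correctly timed. All of that stands.

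Three stronger readings are tempting and not supported:
- A reader might infer that early scores *will* be tested as Day 253 values. The schedule and footnote 13 point that way, but nothing confirms it.
- A reader might infer a breach of SAP 3.4.2, "Unless otherwise specified, missing values will not be imputed". An ET score is an observed value. A wrong label makes it mistimed, not imputed, and that section is not contradicted.
- A reader might take the shrinkage percentages as the expected bias. They are percentages of an unknown change under an assumed straight line. Protocol 1.3 does not expect most clinical measures to be significantly affected by the 3 months of dosing in Part 1.

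**Conclusion.** The gap is real but minor. The plan states a rule that, on the natural reading of the schedule, would place Day 29 to Day 113 values in the Day 253 summaries and tests. This is a visit-timing error of 140 to 224 days for patients who stop during treatment and decline follow-up. The related Week 17 error is 28 to 84 days for those who stop before the last planned dose. The result rests on two conditions: ET visits share the Week 37 label, and at least one such patient exists. One patient would be about 8 to 17% of a planned group, slightly less with replacement. These are exploratory comparisons in a Phase 1 study whose sample size has no statistical basis, so this is a rule to tighten, not a threat to the trial's conclusions.

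**What to change.** Add to SAP 3.2.4:

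> Results from a Part 1 Early Termination visit, or from a Week 17 visit brought forward after early treatment discontinuation, are assigned by actual study day to the scheduled visit whose protocol window contains that day and at which the assessment is planned. They are summarised or tested at Day 253 only if collected within Day 253 ±7 days. Otherwise they are listed and excluded from by-visit tables and tests. This applies to all by-visit data (clinical scales, CSF biomarkers, laboratory tests, vital signs and ECG); worst-value, shift and any-time post-baseline safety summaries still use all results.

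Covering both routes matters: two patients stopping after dose 2 and both seen near Day 57 should be handled alike.

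**Cost.** One paragraph, with no added visits or samples. The downside is that some early-stop values appear in listings only. Counting each possible last dose by each of the four scales at a 4-week visit:
- 4-dose regimen: 0 of 4 match a planned row at Day 29, 2 of 4 at Day 57 (RBANS, MMSE), 0 of 4 at Day 85 and 4 of 4 at Day 113. That is 6 of 16 kept and 10 listed only.
- Cohort D, 2-dose: 0 of 4 at Day 29 and 4 of 4 at Day 113. That is 4 of 8 kept.
- CSF: 4 of 4 possible days match in Cohorts A and B, 3 of 4 in C and 0 of 2 in D.
- Chemistry, hematology, urinalysis and ECG lose little. They are planned at Days 28, 56, 84 and 113 (Days 29, 57, 84 and 113 in Cohort D), so every case in the table above falls in a scheduled window.

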Appendix A Schedule of Procedures – MAD Part 1, all Cohorts Continued

- 4 APP, PSEN1, PSEN2, APOE, BCHE, IL1RAP and MAPT H1 haplotype (unless tested previously and laboratory report is available for documentation)
- 5 Height measured at Screening only
- Full physical and neurological exam (including fundi) to be given at Screening and abbreviated physical (but full neurological) exam to be given during treatment and follow-up period as indicated to assess changes from Screening. In addition to administration on the visits shown, neurological exam should be conducted if patient experiences an adverse event suggestive of cognitive or motor dysfunction
- 7 Measured in triplicate at the Day 1 visit (pre-dose only)
- 8 Women who are not surgically sterile
- 9 In addition to administration on the visits shown, RBANS and MMSE should be administered if the patient experiences an adverse event suggestive of cognitive or motor dysfunction
- 10 Stored at -80 °C for follow-up exploration of laboratory findings and/or adverse events (e.g., measurement of cytokine and/or chemokine levels, measurement of additional markers of kidney function, measurement of antibodies) in this or subsequent clinical studies of ISIS 814907
- 11 Local laboratory analysis of PT, INR, aPTT, and platelets must be conducted, and results reviewed prior to performing any LP on the next day during the Treatment Evaluation Period or the same day during the Post-Treatment Period. At Screening, analysis of PT, INR, aPTT, and platelets must be conducted and results reviewed within 2 days prior to the Screening LP
- 12 Local analysis of PT, INR, aPTT, and platelets is only conducted at Day 253 (Week 37) in patients who will undergo CSF sampling at this visit if they missed a previous LP during the study
- 13 CSF sampling will be conducted at Day 253 (Week 37) as part of the ET procedures in only those patients who did not complete all previous CSF samplings in the study
- 14 Each patient will undergo PET imaging with either FDG or Tau. FDG-PET will be performed unless Tau-PET is available and has been approved at the site. As soon as Tau-PET is approved and available at a site, patients should switch to Tau-PET imaging, instead of FDG-PET imaging, for their next scan

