- 15 This footnote is only applicable to A.2. and A.3. Schedule of Procedures: Patients in Cohorts C and D will seamlessly transition from Part 1 to Part 2. Day 253 of Part 1 will correspond to Day -1 in Part 2. All assessments listed in MAD Part 1, Day 253 and LTE Part 2, Day -1 visits must be completed at this visit; duplicative assessments only need to be done once

Time (in reference to time of Study Drug administration):

- a Pre-dose and 3 hours post IT bolus injection; conduct at 6 hours post IT bolus injection if the patient will be discharged from the clinic on this day (discharge is not permitted on Day 1; discharge is permitted on the other dosing days)
- b 24 hours after prior dose of Study Drug
- c Pre-dose, 3 and 6 hours post IT bolus injection
- d Pre-dose
- e Pre-dose, 0.5, 1, 2, 3, 4, 5, 6, 8, and 12 hours post IT bolus injection
- f Pre-dose, 0.5, 1, 2, 3, 4, and 5 hours post IT bolus injection

Protocol 7 August 2020

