3.5.7 Vital Signs Measurements

Vital signs will include heart rate, respiratory rate, body temperature, body weight, seated and standing systolic and diastolic blood pressure and pulse, and orthostatic changes.

Orthostatic changes include 3 variables: change from seated systolic blood pressures to average of all available standing systolic blood pressures, change from seated diastolic blood pressure to average of all available standing diastolic blood pressure, and change from seated heart rate to average of all available standing heart rate.

Summary tables will be created for the MAD and LTE Periods separately to present the descriptive statistics for vital sign values as well as the change and percent change from baseline at each post-baseline visits.

3.5.8 12-Lead Electrocardiograms (ECG)

Safety 12 lead ECG will be performed in triplicate at the visits indicated in the protocol Schedule of Procedures. ECG data will be collected through a central reader.

The ECG data will include ventricular rate (VR), PR interval, QRS duration, QT, QTcF (QT corrected using the Fridericia's formula), and QTcB (QT corrected using the Bazett's formula).

QTcF and QTcB will be calculated based on the subject's reportable ECG data at each time point using the formula described below:

QTcF = QT / (RR)
$$^{1/3}$$
, where RR = 60 / VR

$$QTcB = QT / (RR)^{1/2}$$
, where $RR = 60 / VR$

At Screening visit, three replicates of ECG parameters will be recorded, and the mean from all replicates will be used as the patient's reportable value at Screening visit. Only calculated QTcB and QTcF will be summarized and included in the data listing. The QTC value recorded on the CRF will not be summarized and will be excluded from the data listing.

For the continuous variables, the average of measurements at a given visit will be used for analysis. For overall interpretation, the worst categorical results of triplicate results and the associated findings will be used for analysis. Summary tables will be created for the MAD and LTE Period respectively to present the descriptive statistics of the actual values, the change and percent change from baseline at each study visit for continuous variables above; and counts and percentages at each study visit for categorical responses to overall interpretation.

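### If visit labels identify only the day, SAP 3.2.4 averages dosing-day vital signs across times around the injection, so the by-visit tables can shrink a short-lived post-dose change

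*Combined protocol and SAP*

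**What the plan says.** SAP 3.2.4 (Analytical visits) sets the level of every by-visit table: "All post-baseline data will be summarized using the visit labels provided in the data". For repeated results it adds: "Multiple results with the same visit label will be averaged for the continuous variables". It makes no exception for readings scheduled at different times within a day, and it does not say whether a label carries the hour.

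SAP 3.5.7 (Vital Signs Measurements) plans, for the MAD and LTE Periods separately, "descriptive statistics for vital sign values as well as the change and percent change from baseline at each post-baseline visits". It names no time point, takes no worst value and sets no outlier threshold. Protocol 10.6.2 adds only that vital signs are tabulated by treatment group.

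The timing note in Protocol Appendix A for vital signs on dosing days reads "Pre-dose, 3 and 6 hours post IT bolus injection". The same note appears in the Part 1 and Part 2 schedules. For blood pressure (BP) and heart rate (HR), footnote 7 in both parts adds "Measured in triplicate at the Day 1 visit (pre-dose only").

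The baseline definitions decide which of these readings count as post-baseline. For the MAD Period, SAP 3.2.3.1 uses the "average of the triplicate values collected on Day 1 pre-dose in the MAD" for BP and HR. For LTE analyses, SAP 3.2.3.2 states: "Active treatment period baseline is the same as the MAD baseline for early start subjects". Late starters (placebo in Part 1) instead take the LTE Day 1 pre-dose triplicate.

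**The concern.** The 3-hour and 6-hour readings are there to show what happens to vital signs after the injection. The schedules list no vital signs on the day after dosing, so these two readings are the only scheduled ones close to each dose. If they are averaged with each other, and on most dosing days with the pre-dose reading, a change that comes and goes within hours is reduced in the table meant to show it.

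The rest of the SAP makes this more noticeable. Plasma concentrations (SAP 3.6.2) are summarised by day and also by scheduled time. Laboratory data (SAP 3.5.6) have outlier criteria and shifts to the minimum and maximum. QTc (SAP 3.5.8) has thresholds applied to the worst post-baseline value. Vital signs have none of these, so the visit mean is their only planned summary. Safety and tolerability are the primary objective of this first-in-human study, and planned active groups are small: three quarters of 8, 8, 12 and 16 patients, or 6, 6, 9 and 12.

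**Working it through.** The plan states no figure on this point, so there is nothing to reproduce. The check counts the readings that fall under one label and works out how much of a post-dose change survives averaging.

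**Inputs**
- Dosing days (Protocol 8.1): MAD Days 1, 29, 57 and 85 for the 4-dose regimen, or Days 1 and 85 for the 2-dose regimen; LTE Days 1, 85, 169, 253 and 337.
- Scheduled times per dosing day (Appendix A timing note): pre-dose, 3 h and 6 h.
- Replicates (footnote 7): three pre-dose BP and HR readings on Day 1 of each part. I take one reading at every other time.
- Scope (SAP 3.2.4): post-baseline results only.
- Baseline (SAP 3.2.3): MAD Day 1 pre-dose for the MAD Period. For LTE analyses, early starters keep that baseline and late starters use LTE Day 1 pre-dose.
- Assumption: labels identify the day and not the hour.

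**Formula**
Let *k* be the number of post-baseline readings under one label and *m* the number of them that show a change of size δ, with the rest at baseline. The tabulated change is (m/k) × δ. For illustration I assume δ = 15 mmHg.

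**Counting k**
- Later dosing days: the pre-dose, 3 h and 6 h readings are all post-baseline, so k = 3.
- MAD Day 1, and LTE Day 1 for late starters: the pre-dose readings are baseline and drop out, so k = 2.
- LTE Day 1 for early starters, BP and HR: the pre-dose triplicate is post-baseline, so a flat mean has k = 3 + 2 = 5. If the triplicate is first reduced to one value, k = 3.

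**Results**

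| Dosing day | k | Change at one post-dose time (m = 1) | Change at both (m = 2) |
|---|---|---|---|
| MAD Days 29, 57, 85 (4-dose) or Day 85 (2-dose); LTE Days 85, 169, 253, 337 | 3 | 1/3: 15 shown as 5.0 | 2/3: 15 shown as 10.0 |
| MAD Day 1; LTE Day 1, late starters | 2 | 1/2: 15 shown as 7.5 | 2/2: 15 shown as 15.0 |
| LTE Day 1, early starters, BP and HR, flat mean | 5 | 1/5: 15 shown as 3.0 | 2/5: 15 shown as 6.0 |
| LTE Day 1, early starters, triplicate averaged first | 3 | 1/3: 15 shown as 5.0 | 2/3: 15 shown as 10.0 |
| Any day, if labels include the scheduled time | 1 | 15 shown as 15.0 at that time | 15 shown as 15.0 at each time |

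The first row covers 3 of 4 MAD dosing days under the 4-dose regimen, 1 of 2 under the 2-dose regimen, and 4 of 5 LTE dosing days.

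**Are the labels day-level?**
Two things suggest so. Footnote 7 treats Day 1 as the visit and pre-dose as a moment within it, and the SAP names a scheduled time in addition to the day for plasma concentrations but not for vital signs. Neither settles the matter.

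**The case against.** The strongest reply is that SAP 3.2.4 uses whatever labels the data carry, and the data specification is not in these documents. If the labels include the hour, nothing is diluted. Some text leans that way. SAP 3.7.1 attaches a pre-dose qualifier to the LTE Day 1 visit. The BP and HR baselines require the data to tell pre-dose from later readings. SAP 3.5.8 uses visit-level averaging for ECG triplicates, which fits a rule meant for replicates. This stands as a reason to keep the point conditional. It does not close the gap: a separate time-point variable would serve the baseline definition without the label carrying the hour, and SAP 3.2.4 does not limit averaging to replicates.

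The second reply is that group means are not the only route to an acute signal. All eCRF data are listed (SAP 3.1), adverse events are tabulated separately (SAP 3.5.3), and the Formal Safety Monitoring Group reviews vital signs during the study (protocol synopsis). SAP 3.5.7 plans no test on vital signs. All of this stands and limits the consequence to the descriptive tables.

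A reader might infer that the tables would understate every acute haemodynamic effect, on every dosing day and in every dose group. The documents do not support that. On MAD Day 1, and on LTE Day 1 for late starters, which between them include each patient's first active dose, no pre-dose BP or HR reading enters the average, and a change present at both 3 h and 6 h is shown in full. Nor does the 1/5 fraction apply to MAD Day 1, where the triplicate is baseline. It can arise only on LTE Day 1 for early starters.

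**Conclusion.** The point holds conditionally. Read literally and with day-level labels, SAP 3.2.4 and 3.5.7 together blend vital signs taken at different times around the injection. A change at one post-dose time then keeps 1/3 of its size on dosing days after Day 1 of each part, 1/2 on MAD Day 1 and on LTE Day 1 for late starters, and as little as 1/5 for BP and HR on LTE Day 1 for early starters. A change at both times keeps 2/3, all, and 2/5 respectively.

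This rests on three assumptions: labels without the hour (likely, not stated), one reading at each post-dose time, and other readings at baseline. The 1/5 and 2/5 figures also need a flat mean over the triplicate.

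The effect is confined to by-visit descriptive tables. It does not show that a safety signal would be missed, because individual readings, adverse events and safety group review remain. The wording should be corrected because the affected tables are the only planned summary of vital signs and the ambiguity is easy to remove.

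**What to change.** In SAP 3.2.4, limit averaging of continuous results to replicates from the same visit and the same scheduled time point. In SAP 3.5.7, tabulate dosing-day vital signs by scheduled time point (pre-dose, 3 h, 6 h) against the baseline the SAP already defines. Each tabulated mean then describes one time point, and the dilution disappears on every dosing day whatever the labels look like.

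Two additions would be useful but are not needed to correct the rule: change from the same-day pre-dose reading, and each patient's largest post-dose fall and rise.

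The cost is a clause in each section and a few more table rows. No new data are collected and no study procedure changes.
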